	appendix 1)		
	Moderate to severe adverse	Moderate to severe adverse	Moderate to severe adverse events occur in \geq 50 of
	events occur in < 20 % of	events occur in $\ge 20\%$ of	participants.
	participants	participants.	

Table 1: Feasibility and Acceptability Criteria

1. Safety: We developed a safety questionnaire and it will be used to assess adverse events at the end of each week (see appendix 1). Participants will also be asked to report any AEs that occurs during any of the session immediately to the physiotherapist delivering the intervention. The AEs questionnaire was developed based on findings from a scoping review that our team has conducted recently (data has been synthesised but has not been published yet) and guided by a systematic review reporting on safety of non-invasive taVNS [10].

2. Efficacy: Preliminary efficacy will be assessed using outcome measures described in table 2. These outcome measures were chosen following recommendations in current stroke literature regarding standardised sensorimotor measurements in stroke recovery trials [16]. Measurements will be conducted at 3-time points (baseline, post-treatment, and 30 days follow-up)

Efficacy outcomes	Outcome measure
Walking 1. Speed 2. Endurance 3. Gaitrite	10-meter walk test (10MWT) 6-minutes walk test (6MWT) Spatial and temporal parameters of gait
Balance Global Disability Self-efficacy	Brief BESTest [18] Modified Rankin Score (mRS) [19] Stroke Self-Efficacy Scale (SSES) [20].

3. Participants experience with taVNS

Qualitative data will be obtained using a structured interview which will be conducted for each participant after 5 days of the final treatment session provided, using attached interview guide (see Appendix 2).

Statistical analysis: The feasibility will be reported against the criteria in table 1. For efficacy outcomes, a linear mixed model analysis will be used to compare two groups (active and sham) and 3-time points (baseline, post-intervention, and follow-up). Safety outcomes will be summarised descriptively. Qualitative interviews will be analysed and reported using thematic analysis. The effectiveness of the sham method in blinding participants will be assessed using a blinding questionnaire which was developed based on the work of Bang et al. (2010) [21] (see Appendix 3) that we developed, and results will be summarised descriptively.

References

- 1. Economics, D.A., *The economic impact of stroke in Australia*. 2020.

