The effect of non-invasive auricular vagus nerve stimulation paired with rehabilitation on gait and balance impairments in chronic stroke: A randomised controlled feasibility trial.

Primary investigator: [name] **Primary Supervisor:** [name] **Co-Supervisors:** [name], and [name]. [name], [name]

Innovation, Implementation and Clinical Translation (IIMPACT) in Health, Allied Health and Human Performance, University of South Australia

Background

Stroke is a leading cause of disability in Australia, costing the economy \$6.2 billion of direct cost and \$26 billion of indirect cost from lost wellbeing and mortality in 2020 [1]. Recovery from stroke mainly occurs in the subacute stage, driven by a period of enhanced neuroplasticity [2]. However, a large proportion of stroke survivors endure long-term impairments including limb weakness, impaired mobility and balance [1]. Hence, there is an imminent need for novel treatments to enhance stroke recovery. Recently, promising studies have demonstrated that pairing invasive vagus nerve stimulation (iVNS) with rehabilitation can enhance motor function post-stroke. For example, a multicentred, triple-blind, randomized controlled trial that included 106 stroke survivors with upper limb weakness has shown that iVNS paired with repetitive task training (for 6 weeks, 3 x 1 hour weekly) led to greater upper limb recovery compared to sham treatment [3]. Interestingly, the improvement in the active group was two to three times higher than the sham group, and more importantly, this effect was preserved for 90 days after treatment. Following this study, iVNS received approval from the Food and Drug Administration (FDA) as adjuvant therapy for chronic stroke rehabilitation [4]. However, iVNS is costly and requires a surgical procedure, limiting accessibility and imposing potential safety risks including symptomatic bradycardia, localised infection, and transient vocal cord palsy [3, 5, 6].

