Transauricular vagus nerves stimulation (taVNS) has been used successfully as a non-invasive, and potentially, safer alternative to iVNS as an adjuvant therapy for drug-resistant epilepsy and major depression [7, 8]. Recently, taVNS paired with rehabilitation was found to be a feasible and safe approach to improve upper-limb weakness in subacute [9] and chronic [6, 10] stroke. The first-in-human pilot study investigating taVNS to enhance upper-limb recovery in 14 adults with chronic stroke was conducted in 2017, showing that taVNS paired with robot-assisted rehabilitation was safe and feasible with effects in favour of the active compared to the sham group [6]. Similar results were observed in subacute stage of ischaemic stroke where taVNS paired with conventional rehabilitation improved upper-limb weakness in 21 people who received 30 minutes of taVNS followed by 30 minutes of conventional therapy for 15 consecutive days [9]. More importantly, the effect of taVNS was preserved 10 weeks from the end of the intervention. Although these early taVNS studies in stroke shared some key limitations, including small sample size, the use of different stimulation parameters, and different sham protocols, their promising results, along with the good quality evidence for iVNS in stroke recovery, warrants further exploration of taVNS role in enhancing stroke recovery.

Altered gait and balance dysfunction are two common stroke-related deficits. Gait dysfunction occurs in more than 80% of people with stroke [11]. This leads to difficulty with mobility and performing activities of daily living [12]. Impaired balance is also common after stroke with 70% of people reporting a fall within 1 year of their stroke [11]. The positive effect of taVNS on upper-limb motor function, likely driven by enhanced neuroplasticity [13, 14], suggests that pairing taVNS with other therapies might prove beneficial. However, the effect of taVNS combined with gait/balance training to enhance recovery of the lower limb has not been studied. This research aims to assess the feasibility, safety, and preliminary efficacy of taVNS

paired with rehabilitation for enhancing gait and balance impairments in people with chronic stroke (> 6 months).

Method:

Aim: The primary aim is to assess the feasibility and safety of taVNS to enhance gait and balance impairments in people with chronic stroke. The secondary aim is to gain preliminary data about the efficacy of taVNS in this population.

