The stimulation will be provided using the tVNS[®] R device (tVNS Technologies GmbH, Reichenschwand, Germany). Stimulation intensity will be individually adjusted to a level that is above the individual's sensory threshold and below pain threshold (tolerable stimulus). A pulse width of 0.3 ms, a frequency of 25 Hz, and a pulse pause ratio of 30 sec on: 30 sec off will be used. The electrode will be placed at left ear, specifically at cymba concha. Participants will not be aware of the stimulation condition they are receiving for the duration of the treatment.

Randomisation, blinding, and concealment:

Participants will be assigned a number from 1 to 40 and allocation to intervention (active or sham taVNS) will be randomised (1: 1 ratio). Randomisation will be completed using the web application available at https://www.randomizer.org/. Subjects will be enrolled in consecutive order.

All participants will not be aware of the stimulation condition they are receiving for the duration of treatment. The sensory and pain threshold for taVNS stimulation will be measured for all participants in the first assessment session (baseline measures) and participants will be familiarised with the taVNS device. Prior to randomisation, all participants will be told that" In this study, we will use different stimulation parameters for different groups of participants. Depending on the parameters used in the group that you will be assigned to, you may feel the stimulus, normally a tingling/prickling/stinging/warmth/vibration sensation at the stimulation site, or feel nothing at all".

The physiotherapist who will provide the intervention will receive a sealed randomisation envelope imprinted with participants' numbers and will provide the appropriate intervention as indicated. The outcome assessor will be blinded.

Outcome Measures: A variety of outcome measures will be used throughout this study as follows:

1. Feasibility: This will be determined by measuring compliance to intervention, adverse events, patient satisfaction, and effectiveness of blinding using criteria described in table 1.

	Proceed	Proceed with Protocol	Significant Amendments Required
		Amendments	
	50% of eligible participants	40% of eligible participants	25% of eligible participants consent to participate
Criteria	consent to participate	consent to participate	
	60% of participants complete	40% of participants complete	25% of participants complete the intervention

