Appendix 1. Symptoms and Adverse Events Following Non-invasive Auricular Vagus Nerve Stimulation

Participant ID: _____

Date: ______

		Severity	,		Persistence	Relatedness	
Symptom/Adverse Event	Tick on	e box per sy Mild	vmptom Moderate	Severe	Tick if symptom persisted after stimulation ceased (please detail duration of symptoms)	Tick if you believe that symptom is related to stimulation	Additional Comments
Redness/erythema							
Pain							
Irritation							
Ulcer							
Itching							
Dizziness							
Headache							
Fatigue							
Increased tinnitus							
Nausea							
Other events (please describe)							

22 November 23, Version 2

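### The only adverse-event progression criterion pools moderate with severe events and ignores seriousness, so its row still reads Proceed with 7 of 40 participants having severe events

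*Protocol*

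**What the plan says.** The Aim paragraph under Method states: "The primary aim is to assess the feasibility and safety of taVNS to enhance gait and balance impairments in people with chronic stroke". Under Outcome Measures, adverse events are one of the measures by which feasibility is to be determined against Table 1.

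Table 1 has one row on harm. It counts participants in whom "Moderate to severe adverse" events occur, and the Proceed column applies when these "events occur in < 20 % of" participants. The middle column starts at 20%. No column separates severe from moderate events, and none mentions seriousness or relatedness.

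The weekly form in Appendix 1 is finer than the rule. It has separate columns for mild, moderate and severe, asks about persistence, and carries the instruction "Tick if you believe that symptom is related to stimulation". It has no field for seriousness, and the protocol does not use the term serious adverse event. Outside Table 1, the Statistical analysis paragraph gives safety a descriptive summary only, with no decision attached.

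**The concern.** Table 1 is the only place where adverse events are turned into a progression decision. Its row gives a moderate itch and a severe event the same weight, and it reacts only to how many participants are affected. A small number of severe events therefore cannot move it.

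Intensity and seriousness are also different things. An event that leads to a hospital admission may be graded mild in intensity, and it would then fall outside the count altogether. At stake is whether the prespecified safety criterion can reflect the events that would matter most to a decision on a larger trial.

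**Working it through.** **Inputs**
- Number of participants: 40, from the Randomisation section ("Participants will be assigned a number from 1 to 40 and allocation to intervention"). As a check, 36, which is 2 × 18 from the Power and sample size paragraph.
- Threshold: Proceed if the proportion with a moderate or severe event is below 20% (Table 1).
- The protocol gives no calculation behind the 20%, so there is no figure to reproduce.

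**Largest count that still reads Proceed**
- N = 40: 0.20 × 40 = 8. A count of 8 is exactly 20% and leaves Proceed, so the maximum is 7, and 7/40 = 17.5%.
- N = 36: 0.20 × 36 = 7.2, so the maximum is again 7, and 7/36 = 19.4%.
- One participant with a severe event is 1/40 = 2.5%, which has no effect unless at least 7 others already count.

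The rule does not look at the grade within the pooled category, so all 7 could be severe.

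**Serious events**

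The count of 7 limits only participants whose events are graded moderate or severe. A serious event graded mild adds nothing to the numerator, so no number of such events changes the row.

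**Chance that the row reads Proceed (illustration)**

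Let X be the number of participants with a severe event, binomial with n = 40 and rate p, and assume that no other event qualifies. Then P(Proceed) = P(X ≤ 7) = Σ C(40,k) p^k (1−p)^(40−k), for k = 0 to 7.

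| Assumed severe-event rate p | P(Proceed), n = 40 | P(Proceed), n = 36 |
|---|---|---|
| 10% | 0.958 | 0.976 |
| 15% | 0.756 | 0.838 |
| 20% | 0.437 | 0.566 |

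The rates are assumptions, since the protocol gives no expected rate of severe events. Moderate events would add to the count and lower these probabilities.

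**How often a review triggered by any severe event would be needed**

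P(at least one) = 1 − (1 − p)^40. For p = 2% this is 1 − 0.98^40 = 0.55. For p = 10% it is 1 − 0.90^40 = 0.985.

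**The case against.** The strongest reply is that this is a design preference. No passage is contradicted and no stated figure is wrong. A pooled count is a coarse but readable feasibility criterion, and safety is also a separately listed outcome. Severe events would be visible: Appendix 1 separates them from moderate ones, it has room for other events and comments, and events during sessions are to be reported at once to the physiotherapist. This stands as far as the severity data go. It does not supply a decision, because the descriptive summary leads to none and the row that does lead to one discards the grade. Nor would a statistical analysis plan or external event reporting change the row, since the threshold is fixed in this protocol.

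A second reply is that 40 people cannot reveal rare harms under any rule: a harm with a true rate of 1% is absent from 0.99^40 = 67% of such trials. That is correct. The point here concerns severe or serious events that do occur and then have no effect on the row.

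Several stronger readings are tempting and are not supported:
- A reader might infer that the trial as a whole would be told to proceed. The harm row is one of seven in Table 1, and the protocol does not say how rows combine.
- A reader might take 7 as the limit on serious events. It limits only events graded moderate or severe.
- A reader might say that the rule tolerates events caused by stimulation. The row counts all events, related or not.
- A reader might cite the Background ("imposing potential safety risks including symptomatic bradycardia, localised infection, and transient vocal cord palsy") as the harm that the rule would miss. That sentence describes implanted, surgical stimulation. The protocol presents the auricular form as potentially safer and names no grave harm of it.

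**Conclusion.** The point holds as a weakness in a stated rule. With 40 participants the adverse-event row reads Proceed with up to 7 participants (17.5%) having severe events, and it sets no limit on serious events because seriousness is not recorded. The limit of 7 is the same with 36 participants and depends only on the threshold and the number enrolled. The probabilities 0.96 and 0.76 rest on assumed severe-event rates of 10% and 15%, with no other qualifying events, and are illustrations only. Nothing in the protocol suggests that severe events are likely. The change is cheap and worth making because safety is part of the primary aim.

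**What to change.** - **Keep the present moderate-to-severe row unchanged.** All severe events then still count towards the 20% threshold, whether or not they are judged related. Restricting that row to moderate events, with only related severe events in a new row, would leave severe events judged unrelated in neither row.
- **Add one row to Table 1 for severe or serious events.** If any such event occurs, Proceed is not returned automatically. A documented case review then decides which column applies. Relatedness should be judged by someone unaware of allocation, because the treating physiotherapist opens the allocation envelope and the form records only the belief of whoever completes it. The review settles the column, so one severe but trivial symptom does not force a downgrade.
- **Add a yes/no box for seriousness to Appendix 1**, with its definition stated, so that seriousness is not inferred from intensity.

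This is a criterion for progression to a later trial and does not alter the treatment of participants. It needs no extra participants or visits. The cost is one table row, one box on the weekly form, a short case review when a severe or serious event occurs, and a possible loss of an automatic Proceed. If the true severe-event rate were 2%, an assumed figure, severe events alone would trigger the review in about 55% of trials of this size.

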Study Design: This will be a randomised double-blinded sham-control trial. Participants will be assessed at baseline, immediately post, and at \geq 30 days after completing the intervention.

Participants:

Participants will be recruited from the UniSA Health and Medical Clinic as well as advertising at Stroke SA, Stroke Foundation and via social media. All assessments and treatments will be conducted within the UniSA Health and Medical Clinic at the City West.

Power and sample size: A power calculation is not necessary for a feasibility study; further no studies have investigated the use of taVNS for enhancing gait and balance. However, to provide some insight, we have performed a power calculation based on effect sizes obtained from a previous upper limb taVNS study [10]. It was determined that 18 participants will be required (in each group) to detect a moderate effect size of 0.70, given an alpha level of 0.05 and power of 80 % [15].

Inclusion criteria: Aged 18 years or older; first-ever haemorrhagic or ischaemic stroke at least 6 months earlier; can walk 10 meters with or without a gait aid and with or without assistance (assessed using 10-meter walk test [16]), no history of other neurological conditions; gait and/or balance impairment; ability to give informed consent and to understand instruction.

Exclusion criteria: Previous vagus nerve surgery; cognitive impairment and/or language impairment that might impact the person's ability to consent or understand instructions (MOCA score of less than 18); severe pain in any joints of the affected limb; advanced cardiac, pulmonary, kidney or liver condition; pregnancy; use of neuroactive medication [6]; active implants; cerebral shunts; open skin at the point of stimulation.

Intervention: The physical rehabilitation therapy component of the intervention will be tailored to participants' impairments and goals. It will consist of 15 sessions conducted over 6 weeks (2-3 x 1-hour sessions per week). Concurrently with the physical rehabilitation, participants will receive one of taVNS conditions (active or sham, allocation will be randomised).

taVNS stimulation parameters:

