	all the sessions of the	the intervention protocol	protocol
	intervention protocol		
	50% found intervention useful	25% found intervention useful	$< 25\%$ found intervention useful (Likert $\ge 4/5$)
	$(Likert \ge 4/5) [17]$	$(\text{Likert} \ge 4/5)$	
	50% found intervention helpful	25% found intervention helpful	$< 25\%$ found intervention helpful (Likert $\ge 4/5$)
	$(\text{Likert} \ge 4/5)$	$(\text{Likert} \ge 4/5)$	
	50% found intervention	25% found intervention	< 25% found intervention delivery acceptable
	delivery acceptable (Likert \geq	delivery acceptable (Likert \geq	(Likert $\geq 4/5$)
	4/5)	4/5)	
	Blinding \geq 90% (Assessed	Blinding $\geq 50\%$	Blinding < 50%
	using a blinding questionnaire		
	that we developed, see		

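### The Table 1 adverse event criterion names neither arm nor relatedness, so as worded it pools active and sham participants and can pass a high event rate confined to active taVNS

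*Protocol*

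**What the plan says.** The Aim paragraph makes feasibility and safety of taVNS the primary aim, and the Statistical analysis paragraph says that feasibility is reported against Table 1.

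The adverse event row of Table 1 has three levels:
- Proceed, if moderate to severe "events occur in < 20 % of" participants.
- Proceed with protocol amendments, from 20% upwards.
- Significant amendments required, from 50 upwards, which I read as a percentage. This cell begins "Moderate to severe adverse events occur in".

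No level mentions an arm or a relatedness condition. The section on Randomisation, blinding, and concealment states: "Participants will be assigned a number from 1 to 40". The same sentence sets equal numbers for the active and sham arms.

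The Safety paragraph says of the questionnaire that "it will be used to assess adverse events at the end of each week". The form in Appendix 1 lists pain, dizziness, headache, fatigue and nausea among its symptoms. It has severity columns and a relatedness column headed "Tick if you believe that symptom is related to stimulation". Table 1 does not refer to that column.

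The satisfaction rows, for example "50% found intervention useful", also name no arm. They give no denominator.

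**The concern.** The row is meant to judge whether taVNS is safe enough to take forward, but half of the people in its denominator never receive active taVNS. If stimulation causes moderate or severe events and sham does not, the sham arm adds to the denominator and nothing to the numerator. A cut-off of 20% of participants is then a much laxer limit on the people actually stimulated.

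Because relatedness plays no part, the row also counts symptoms that have nothing to do with stimulation. The checklist is repeated weekly during a course of physical rehabilitation in chronic stroke survivors, and several of its items are non-specific.

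At stake is the progression decision on a primary aim. The row could return Proceed when active stimulation is often poorly tolerated, or call for amendments when stimulation adds nothing.

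**Working it through.** **Inputs from the protocol.** 40 participants allocated 1:1, so 20 active and 20 sham; cut-offs at 20% and 50%; 15 sessions over 6 weeks with a weekly form, so about six forms each. The 20% cut-off is a chosen value with no derivation to reproduce. **Assumed, because the protocol gives no event rates:** true active-only rates of 20% to 40%, and background rates of 5% to 30% per participant.

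**1. Where the lines fall.** 0.20 × 40 = 8, so the pooled row reads Proceed with up to 7 affected participants. Scored on the active arm, 0.20 × 20 = 4, so it reads Proceed with up to 3.

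**2. Dilution.** With equal arms, pooled rate = (active rate + sham rate) / 2. If the sham rate is zero, the 20% line corresponds to 40% of the active arm, and the 50% line to 20 of 20. Seven active and no sham participants affected gives 7/40 = 17.5%, which is Proceed. In the active arm alone this is 7/20 = 35% (exact 95% CI 15% to 59%). Fisher's exact test of 7/20 against 0/20 gives p = 0.008.

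**3. Chance of Proceed when only active participants have events.** Let X be binomial with n = 20 and the true active rate. The pooled row passes if X ≤ 7, the active-arm row if X ≤ 3.

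| True active rate (sham 0) | Pooled row | Active-arm row |
|---|---|---|
| 20% | 0.97 | 0.41 |
| 25% | 0.90 | 0.23 |
| 30% | 0.77 | 0.11 |
| 35% | 0.60 | 0.04 |
| 40% | 0.42 | 0.02 |

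With 36 participants, the 18 per group in the sample size paragraph, 0.20 × 36 = 7.2, so the pooled row still trips at 8. Up to 7/18 = 39% of the active arm could then be affected and the row would pass.

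**4. How far dilution depends on a quiet sham arm.** Seven active events plus one sham event is 8/40 = 20%, no longer Proceed. A 35% active rate with a 10% sham rate pools to (35 + 10)/2 = 22.5%, also above the line.

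**5. Background symptoms alone.** Assume the same rate in both arms and no stimulation effect. The pooled row trips with probability P(at least 8 of 40), an all-cause active-arm row with P(at least 4 of 20).

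| Background rate per participant | Pooled row trips | Active-arm row trips |
|---|---|---|
| 5% | 0.001 | 0.02 |
| 10% | 0.04 | 0.13 |
| 15% | 0.24 | 0.35 |
| 20% | 0.56 | 0.59 |
| 25% | 0.82 | 0.78 |
| 30% | 0.95 | 0.89 |

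If weeks were independent, a weekly chance w would accumulate to 1 − (1 − w)^6, which reaches 20% at w = 1 − 0.8^(1/6) = 3.7%. Symptoms that recur in the same people would give a lower cumulative share for the same weekly rate.

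**The case against.** Table 1 does not say in words that arms are pooled or that any cause counts. It is silent on both, and the heading of Appendix 1 refers to events following stimulation. Safety is to be summarised descriptively, which does not rule out tables by arm, and a statistical analysis plan could add them. This stands as a caution: pooling is the plain reading of participants in a trial whose participants are numbers 1 to 40 across both arms, but it is inferred. It does not remove the point, because the progression cut-off and its denominator are set in the protocol, and a descriptive table by arm would leave that rule unchanged.

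The two failures also pull against each other. Exact halving needs no sham events, while background tripping needs many events in both arms. The 7 against 0 split is the most extreme that still passes. All of this stands, so a reader should not infer that active harm is always halved.

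A reader might also infer that background symptoms will trip the row. The protocol gives no rate, and at 10% or less per participant tripping is unlikely.

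Finally, a reader might extend the criticism to the satisfaction rows. The documents do not support that as an error. Those rows state no denominator, the intervention includes physical therapy given to both arms ("The physical rehabilitation therapy component of the intervention will be tailored to participants' impairments and goals"), and acceptability of the whole package in both arms matters for running a sham-controlled trial. Pooling there is defensible.

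**Conclusion.** The point holds for the adverse event row. As worded, its cut-offs apply to active and sham participants together and ignore relatedness, so events confined to active taVNS are diluted. The dilution is exactly twofold under 1:1 allocation with no sham events and smaller as sham events appear. In the zero-sham case, an active arm with 35% affected passes a 20% limit, and a true 30% active-only rate passes about three times in four.

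The opposite error, tripping on background symptoms, is possible but conditional on a rate that the protocol does not give. Its probability runs from negligible at 5% per participant to more than one half at 20%.

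Table 1 is an end-of-study progression guide, not a stopping rule. The consequence is therefore a misleading decision about the next trial rather than a gap in protecting participants during this one. The change should be made, and it is a small one.

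**What to change.** Reword the adverse event row so that the existing cut-offs apply to the active arm. Report the sham rate and the active-minus-sham difference with its 95% CI beside it. Report all-cause and stimulation-related events separately, state in advance which of the two the cut-off uses, and read the result against the sham rate. The relatedness item is already collected, so no new data are needed.

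The costs are wider intervals on 20 rather than 40 participants and, if the cut-off uses all-cause events, a higher chance of tripping from background symptoms at low rates (0.13 against 0.04 at 10%). Moving to the active arm cures the dilution but not the background noise. For that reason the choice of event type and the comparison with sham must be part of the rule.

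As a secondary suggestion only, report the satisfaction rows by arm as well.
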